5.5.8.2. Gated Secondary

The gated secondary outcome, 50% response, is the proportion of patients meeting the response criteria at Week 3. A nonresponder imputation for missing values will be used. Specifically, all patients who discontinue study treatment at any time prior to Week 3, for any reason, will be considered a nonresponder.

Treatment differences in the proportions of patients meeting 50% response definition at Week 3 will be determined using Koch's Nonparametric Randomization-Based Analysis of Covariance method (Koch et al. 1998). This method will adjust for pooled investigative site by including it as a stratification variable and will also adjust for the continuous baseline value and gender. A SAS/IML macro (NParCov3) (Zink and Koch 2012) will be used for the calculation. The options with this SAS/IML macro are specified in the example SAS code below.

```
%NPARCOV3( outcomes =[response]
covars = [baseline] [gender]
trtgrps = [treatment]
strata = [PINVID]
hypothesis = NULL
transform = NONE
combine = FIRST
c = 1
dsnin = [input]
dsnout = [output])
```

In this method, the option of “hypothesis=NULL” indicates that the variance covariance structure will be calculated under the assumption that the means and covariance matrices of the treatment groups are equal and therefore computes a single covariance matrix for each stratum. The option of “combine=FIRST” indicates that the covariate adjustment will be performed after a weighted average of treatment group differences across pooled investigative sites to account for the possibility of small numbers of patients at some sites. The option of “c=1” indicates the use of Mantel-Haenszel weights for each pooled investigative site. The option of “transform=NULL” indicates that there is not a transformation of the data.

The analysis result of the secondary gatekeeper objective will be evaluated if the placebo versus GMB300mg comparison is significant for the primary efficacy analysis at a one sided $\alpha=0.025$ significance level.

5.5.8.3. Additional Secondary and Exploratory Efficacy Analyses

Table CGAL.5.3 summarizes all the planned additional secondary efficacy analyses for SP III and SP IV.

For the continuous additional secondary and exploratory efficacy measures, the change from baseline to each postbaseline period will be estimated for each treatment from repeated measures analyses as described in Section 5.5.8.2. The treatment comparison at each week and overall across 8 weeks will be provided. As discussed in Section 5.5.1.1, for the efficacy measures that are not derived from cluster headache frequency, the baseline average daily cluster headache attack frequency category (≤ 4 vs. >4) will be added as a covariate in the MMRM model.

For the categorical additional secondary and exploratory efficacy measures including 30%, 50%, 75% response, and 100% response, the percentage of patients meeting response criteria at each period will be estimated for each treatment from a categorical, pseudo-likelihood-based repeated measures analysis of visit wise binary outcomes indicating whether patients meet response criteria. The treatment comparison at each week and overall across 8 weeks will be provided. This analysis will be implemented using the GLIMMIX procedure in SAS to compare treatments and include the fixed, categorical effects of treatment, gender, visit/week, and treatment-by-visit/week interaction, as well as the continuous, fixed covariate of baseline value. An unstructured covariance structure will be used to model the within-patient errors (denoted by TYPE=CHOL in the RANDOM statement). The Newton-Raphson method with ridging will be used for nonlinear optimization (denoted by including NLOPTIONS TECH=NRRIDG). The Kenward-Roger approximation will be used to estimate denominator degrees of freedom. If the model does not converge, the Fishers scoring algorithm will be utilized by the SCORING option in SAS. If the model still fails to converge, the model will be fit using covariance matrices in the following order specified by a decreasing number of covariance parameters until convergence is met: heterogeneous Toeplitz, heterogeneous autoregressive, Toeplitz, and autoregressive. If necessary, both fitting algorithms will be used in the prespecified order before proceeding to the next covariance structure in the sequence. For models where the unstructured covariance matrix is not utilized, the sandwich estimator (Diggle et al. 1994) will be used to estimate the standard errors of the fixed effects parameters. The sandwich estimator is utilized by the EMPIRICAL option in SAS. When the sandwich estimator is utilized, the Kenward-Roger approximation for denominator degrees of freedom cannot be used. Instead, the denominator degrees of freedom will be partitioned into between-subject and within-subject portions by the DDFM=BETWITHIN option in SAS. As discussed in Section 5.5.1.1, for the efficacy measures that are not derived from cluster headache frequency, the baseline average daily cluster headache attack frequency category (≤ 4 vs. >4) will be added as a covariate in the GLIMMIX model.

Table CGAL.5.3. Other Secondary and Exploratory Efficacy Variables and Their Derivation

Study Phase III	Study Phase IV	Efficacy Variable	Analyses
Change from baseline to each 7-day interval (Weeks 1, 2, 3, 4, 5, 6, 7, and 8)	No planned analysis	1. Weekly cluster headache attack frequency 2. Weekly average cluster headache attack pain severity in the remaining cluster headache attack days 3. Weekly total cluster headache attack duration 4. Weekly number of times using oxygen 5. Weekly number of times using oral triptan, sumatriptan nasal spray, or zolmitriptan nasal spray 6. Weekly number of times using sumatriptan Sc 7. Weekly number of times using acetaminophen/paracetamol or NSAIDs 8. Number of times using oxygen per cluster headache attack 9. Number of times using oral triptan, sumatriptan nasal spray, or zolmitriptan nasal spray per cluster headache attack 10. Number of times using sumatriptan Sc per cluster headache attack 11. Number of times using acetaminophen/paracetamol or NSAIDs per cluster headache attack 12. Total weekly dose of oral sumatriptan, sumatriptan nasal spray and zolmitriptan nasal spray combined 13. Total weekly dose of sumatriptan Sc 14. Total weekly dose of oral sumatriptan 15. Total weekly dose of sumatriptan nasal spray 16. Total weekly dose of zolmitriptan nasal spray	Variables will be analyzed by a repeated measures analysis using a model as described in Section 5.5.8.1 and Section 5.5.8.3.

Other Secondary and Exploratory Efficacy Variables and Their Derivation

Study Phase III	Study Phase IV	Efficacy Variable	Analyses
Value at each visit (Visits 5, 7, corresponding to Month 1, 2)	Value at each visit (Visit 9, corresponding to Month 6)	1. PGI-I Score	For SP III, the variable will be analyzed by a repeated measures analysis using a model as described in Section 5.5.8.3, without baseline covariate. For SP IV, the variable will be analyzed by an ANOVA model as described in Section 5.5.1.1.
Categorical variables at each 7 day period (Weeks 1, 2, 3, 4, 5, 6, 7, and 8)	No planned analyses	1. 30% response 2. 50% response 3. 75% response 4. 100% response 5. 30% reduction in weekly total cluster headache attack duration	For all variables, the visit wise percentages of patients meeting criteria will be compared between treatments using a categorical, repeated measures analysis described in Section 5.5.8.3.
Categorical variables at each visit (Visits 5, 7, corresponding to Month 1, 2)	Categorical variables at each visit (Visit 9, corresponding to Month 6)	1. Proportion of patients reporting a score of 1 (“very much improved”) or 2 (“much improved”) on Patient Global Impression of Improvement (PGI-I)	For SP III, the visit wise percentages of patients meeting criteria will be compared between treatments using a categorical, repeated measures analysis described in this Section 5.5.8.3 but without baseline value covariate. For SP IV, the Koch’s Nonparametric Randomization Based Analysis of Covariance method as described in Section 5.5.8.2 will be used, but adding the baseline average daily cluster headache attack frequency category (≤ 4 vs. > 4) and removing baseline value covariate.

Abbreviations: ANOVA = analysis of variance; NSAIDs = nonsteroidal anti-inflammatory drugs; SP = study phase.

5.5.9. Safety Analyses

The safety analyses will be conducted for SP III in safety population and SP IV in posttreatment population.

The safety and tolerability of treatment will be assessed by summarizing the following:

- adverse events
 - treatment-emergent adverse events
 - by PT
 - by PT nested within SOC
 - by maximum severity
 - treatment-emergent adverse events by PT nested within SOC
 - adverse events leading to discontinuation by PT nested within SOC
 - adverse events of special interest
- suicide-related thoughts and behaviors by CSSRS
- vital signs and weight
- laboratory measurements
- electrocardiograms
- antibodies (ADA and Nab)

The baseline and postbaseline for all safety measures are described in [Table CGAL.5.2](#) unless specified otherwise. For SAEs, only events with a start date during the postbaseline phase will be accounted for the corresponding study phase analysis.

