5.5.1.6. Baseline and Postbaseline Definition

Table [CGAL.5.2](#) describes the rules for determining the patient population and baseline and postbaseline observations for each study phase and type of analysis. When “last of Visit x-x” is used in the table, the last nonmissing observation obtained in the visit interval will be used.

Table CGAL.5.2. Patient Population with Baseline and Postbaseline Definitions by Study Phase and Type of Analysis

Study Phase/Analysis	Patient Population	Baseline Observation	Postbaseline Observation(s)
Study Phase III			
Continuous secondary efficacy analyses (Repeated measures)	Patients in ITT population with a baseline and at least 1 postbaseline observation	Visit 3	All Visits 4-7
TEAEs	Safety population	All Visits 1-3 before dosing	Visit 3 after dosing through Visit 7
SAEs, Discontinuations due to AEs	Safety population	NA	Visit 3 after dosing through Visit 7
C-SSRS categorical analyses	Patients in safety population with a baseline and at least one postbaseline C-SSRS assessment	Recent history: All Visits 1-3 excluding lifetime ^a All prior history: Visits 1- 3 including lifetime ^a	All Visits 3.01-7
TE abnormal laboratory values	Patients in safety population with normal laboratory values at all nonmissing baseline visits (with respect to direction being analyzed) and who have at least 1 postbaseline observation	All Visits 1-3	All Visits 3.01-7
TE immunogenicity	Patients in safety population who are evaluable for TE ADA	Visit 3	All Visits 3.01-7
TE changes in vital signs and weight, ECG parameters	Patients in safety population with a baseline and at least 1 postbaseline observation	Last nonmissing value from Visits 1-3 for BP, pulse, and ECG All Visits 1-3 for weight and temperature	Visits 3.01-7

Patient Population with Baseline and Postbaseline Definitions by Study Phase and Type of Analysis

Study Phase/Analysis	Patient Population	Baseline Observation	Postbaseline Observation(s)
Continuous safety analysis of vital signs, weight, laboratory, and ECG parameters (Box-whisker plot)	Safety population	Last non-missing value from Visits 1-3	Visits 4-7
Study Phase III and IV Combined			
TE immunogenicity	Patients in safety population who are evaluable for TE ADA	Visit 3	All Visits 3.01-9
Study Phase IV			
Post TEAEs	Posttreatment population	All Visits 1-7	All Visits 7.01-9
SAEs, Discontinuations due to AEs	Posttreatment population	NA	All Visits 7.01-9

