5.8. Reports to Be Generated at Each Interim and Final Database Lock

5.8.1.1. Reports to Be Generated at Interim Database Lock

For the interim analysis, the database will be locked after all randomized patients have had the chance to complete 8 weeks of treatment in SP III. However, some patients will still be ongoing in SP IV at the time of the database lock. Data up to the data cutoff date in the locked database from all study phases will be used, and analyses specified in this SAP will be performed. However, only analyses conducted for SP III at interim analysis will be considered as the final

analyses. The analyses including data from SP IV will be rerun and updated when the completed data are available at the final database lock.

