5.8.1.2. Reports to Be Generated at Final Database Lock

For final database lock, all analyses including tables, figures and listings that use data from SP IV will be generated.

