5.9. Clinical Trial Registry Analyses

Additional analyses will be performed for the purpose of fulfilling the Clinical Trial Registry (CTR) requirements. These analyses will be the responsibility of the Sponsor.

Analyses provided for the CTR requirements include the following:

A summary of AEs will be provided as a dataset that will be converted to an XML file. Both Serious Adverse Events and “Other” Adverse Events are summarized by treatment group and by MedDRA PT.

- An AE is considered “Serious” whether or not it is a TEAE.
- An AE is considered in the “Other” category if it is both a TEAE and is not serious. For each “Serious” AE and “Other” AE, for each term and treatment group, the following are provided:
 - the number of participants at risk of an event
 - the number of participants who experienced each event term
 - the number of events experienced
- Consistent with www.ClinicalTrials.gov requirements, “Other” AEs that occur in fewer than 5% of patients in every treatment group may not be included if a 5% threshold is chosen.
- AE reporting is consistent with other document disclosures; for example, the CSR, manuscripts, and so forth.

6. References

Guy W. ECDEU assessment manual for psychopharmacology, revised 1976. Rockville, MD: National Institute of Mental Health, Psychopharmacology Research Branch. p 217-222. Available at: <https://archive.org/details/ecdeuassessmentm1933guyw>. Accessed September 29, 2014.

Permutt T. Sensitivity analysis for missing data in regulatory submissions. *Stat Med*. 2015;35(17):2876-2879.

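### SAEs are tabulated by start date and SP III outputs are frozen at the interim lock, so an event that becomes serious later can fall outside both phase-specific SAE tables

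*SAP*

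**What the plan says.** **Phase assignment.** SAP 5.5.9: "For SAEs, only events with a start date during the postbaseline phase will be accounted for the corresponding study phase analysis". Table CGAL.5.2 (SAP 5.5.1.6) sets the windows for SAEs. SP III runs "Visit 3 after dosing through Visit 7" and SP IV is "All Visits 7.01-9". The only row for the two phases combined is immunogenicity.

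**Locks.** SAP 5.8.1.1 notes that "some patients will still be ongoing in SP IV at the time of the database lock", and that "only analyses conducted for SP III at interim analysis will be considered as the final" analyses. It adds: "The analyses including data from SP IV will be rerun and updated when the completed data are available at the final database lock". SAP 5.8.1.2 says that at the final lock "all analyses including tables, figures and listings that use data from SP IV will be generated". The SAP revision history (Version 4) gives the reason for treating SP III as final: every patient will have finished that phase.

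**Registry.** SAP 5.9 plans a further summary by treatment group and preferred term in which an AE counts as serious "whether or not it is a TEAE". It states no phase, start-date window or lock. It also says that AE reporting is consistent with other disclosures, including the clinical study report.

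**Collection.** Protocol 10.2.1.1 starts SAE collection once investigational product has been given and continues it to the last study visit. An event that is serious before dosing is not reported as serious unless the investigator thinks a protocol procedure may have caused it.

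**The concern.** Seriousness is often reached after onset. Two of the protocol's criteria, hospitalisation and death, are outcomes of an event that may have begun days or weeks before. A rule that uses only the start date says nothing about when the event became serious. A rule that freezes SP III because all patients have completed it deals with new onsets, but not with later changes to events that began there.

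SAEs are a named secondary safety measure in both documents (Protocol 6.2.2, SAP 4.2.2). The events at risk of omission are those that escalate after exposure, which a safety reader most wants to see. The SAE rule is also narrower than the TEAE rule in SAP 5.5.9.1.1, which admits worsening as well as new onset.

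**Working it through.** The plan states no figure to reproduce. The check is to trace each kind of event through the start-date rule, the Table CGAL.5.2 windows and the lock rules. It assumes that the AE record keeps its original start date on escalation.

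| Onset | Becomes serious | SP III SAE table | SP IV SAE table | Registry summary |
|---|---|---|---|---|
| Before dosing | Before dosing | No | No | Only if procedure-related; otherwise not recorded as an SAE |
| Before dosing | After dosing | No: start date precedes the window | No: start date precedes the window | Possible |
| SP III | SP III, or SP IV before the interim lock | Yes | No | Possible |
| SP III | SP IV, after the interim lock | No: table already final | No: start date precedes Visit 7.01 | Possible, if run on final data |
| SP IV | SP IV | No | Yes, at final lock | Possible |

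Rows 2 and 4 are the gap. Row 1 is not a fault of the SAP sentence, because the protocol's collection rule already keeps most such events from being SAEs. Rows 3 and 4 can be clinically identical. Which row applies depends on whether the lock comes before or after the escalation, and so partly on how late the patient was randomised.

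**Do the TEAE tables fill the gap?** Only in part. For row 2, SAP 5.5.9.1.1 judges worsening by severity (mild, moderate, severe). An event already severe at baseline cannot rise further on that scale, so it need not become a TEAE if it later leads to hospitalisation. For row 4, a treatment-emergent event is in the SP III TEAE tables, but without its serious status.

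**Exposed period for row 4.** The study schedule places SP IV between Day 60 and Day 180: 180 − 60 = 120 days (16 × 7 = 112 days by the phase description). A patient is exposed for whatever part of this remains after the lock, and for none of it if already finished. The documents give no lock date, so no probability can be attached.

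**Size.** With *k* true SAEs in an arm, missing one understates the count by 1/*k*. The documents give no expected SAE count, so *k* is an assumption:

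- *k* = 2: 1/2 = 50%
- *k* = 3: 1/3 = 33%
- *k* = 5: 1/5 = 20%

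On the planned 162 patients, an arm is 162/2 = 81, and one patient is 1/81 = 1.2 percentage points. For *k* = 3 (one event per patient), 3/81 = 3.7% would be shown as 2/81 = 2.5%. The SAP revision history says enrolment was stopped early. If the arms are smaller than 81, one patient weighs more.

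**The case against.** The strongest reply is that the events are not lost. Protocol 10.2.1.1 sends SAEs up to the last visit to the clinical database and the pharmacovigilance system, whatever the investigator's view of causality. SAP 5.9 plans an SAE summary that is not limited to treatment-emergent events. This stands in part. A reader might infer that these events appear in no SAE table at all, and the documents do not support that, because the registry summary could hold both kinds. It is not a dependable remedy, however. Its window and lock are unstated, and its stated consistency with the study report could bring the phase rule back in. Nor do the documents show that the registry and phase tables must contradict each other, since a whole-study count and phase counts differ in scope.

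A reader might also infer that every event beginning before dosing drops out. That is too broad, because events already serious before dosing are mostly not SAEs under the protocol.

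The gap also depends on how the case report form works. Protocol 10.2.1 has sites record changes in a patient's conditions. If an escalation opens a new record with a new start date, the start-date rule captures it. The documents do not settle this, so it remains an assumption.

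Finally, assigning phase by the date of seriousness is a tempting remedy but a debatable one. It would move events with SP III onset out of the randomised Fisher comparison and into SP IV, which is descriptive only (SAP 5.5.9.1). This objection stands, and the fix below keeps assignment by onset.

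**Conclusion.** The point holds in a limited form. Under the stated rules, an AE that starts before dosing and becomes serious after it, or that starts in SP III and becomes serious after the interim lock, is in neither phase-specific SAE table. This rests on one assumption, that the AE record keeps its start date on escalation. Only the registry summary could show such an event, and its window and lock are not given.

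Few events are expected, and the documents do not allow a rate to be estimated. The error can only be an undercount, and nothing in the rules treats the arms differently. One event still matters where an arm may have only a handful. The case for changing the plan is that the correction is cheap and the outcome is a stated safety objective.

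Separately, the list of AE summaries in SAP 5.5.9 repeats the line for TEAEs by preferred term within system organ class and has no SAE line, whereas Protocol 12.2.10 has one. That is clerical. SAEs are among the safety endpoints in SAP 5.4.2 and have rows in Table CGAL.5.2, so a reader should not infer that no SAE analysis is planned.

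**What to change.** Keep assignment to a phase by onset, and add two things to the SAP:

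1. At final lock, an all-phase SAE table and listing by treatment group that includes every event meeting a seriousness criterion after the first dose, whatever its start date.
2. A rerun of the SP III SAE table at final lock, with a report of any change in seriousness since the interim lock.

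The SAE line in the SAP 5.5.9 list can be restored in the same edit.

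The cost is one extra table and listing and one rerun. The SP III SAE count may also change slightly after the interim report, so that report should say that its SAE count is subject to update.

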5.5.9.1. Categorical Safety Variables

Unless specified otherwise, the categorical safety analyses will include both scheduled and unscheduled visits and be conducted for SP III and SP IV separately.

Comparisons between treatment groups for all categorical safety measures will be made using Fisher's exact test for SP III with the safety population. Descriptive statistics only will be presented for the treatment groups in SP IV with post-treatment population.

5.5.9.1.1. Adverse Events

Treatment-emergent AEs are defined as the reported AEs that first occurred or worsened during the postbaseline phase compared with baseline phase. For events occurring on the day of first administration of study drug, the CRF-collected flag will be used to determine whether the event was pretreatment versus posttreatment. For each TEAE, the severity level of the event (mild, moderate, or severe) will be determined by patient or physician opinion. The Medical Dictionary for Regulatory Activities (MedDRA) Lowest Level Term (LLT) will be used in the treatment-emergent computation. For each LLT, the maximum severity at baseline will be used as the baseline severity. If the maximum severity during postbaseline is greater than the maximum baseline severity, the event is considered to be treatment emergent for the specific postbaseline period. For events with a missing severity during the baseline period, it will be treated as "mild" in severity; for events with a missing severity during the postbaseline period, it will be treated as

“severe” for TEAE computation. For each patient and TEAE, the maximum severity for the MedDRA level being displayed (PT, High Level Term, or SOC) is the maximum postbaseline severity observed from all associated LLTs mapping to that MedDRA level.

For events that are gender specific, the denominator and computation of the percentage will be gender adjusted.

5.5.9.1.1.1. Potential Hypersensitivity Events

Potential hypersensitivity events will be defined using the following terms (standard MedDRA query [SMQ]):

- Broad and narrow terms in the Anaphylactic reaction SMQ (20000021)
- Broad and narrow terms in the Angioedema SMQ (20000024)
- Broad and narrow terms in the Hypersensitivity SMQ(20000214)

A listing of patients having an event identified from these analyses will be medically reviewed to determine if the terms identified represent events likely hypersensitivity in nature. Listings should include information on timing of event relative to latest dose of study drug administration, the event term from this query, other AEs for the patient and timing, any abnormal laboratory findings, concomitant medication, medical history, and pre-existing conditions. Only those that are judged medically to be events likely hypersensitivity in nature will be included in the final tables.

The number and percentage of patients with potential and/or likely TEAEs will be summarized by treatment groups using MedDRA PT nested within the SMQ. Events will be ordered by decreasing frequency within the SMQ. The number and percentage of patients with likely hypersensitivity SAEs and AEs resulting in study drug discontinuation will be presented by treatment groups using MedDRA PT and ordered by decreasing frequency by PT.

The number and percentage of patients with likely hypersensitivity TEAEs by maximum severity will be summarized by treatment groups using MedDRA PT.

The number and percentage of patients with likely hypersensitivity TEAEs by timing will be summarized using MedDRA PT. Events will be ordered by decreasing frequency of PT. Note the timing of the likely hypersensitivity events is collected through eCRF and categorized into the following 4 categories:

1. Immediate: occurs within minutes (<60 minutes) from study drug administration
2. Acute Reaction: occurs from 1 up to 6 hours from study drug administration
3. Delayed Reaction: occurs from >6 hours through 14 days from study drug administration, which will be split into 2 categories: on the same day of injection and after the day of injection
4. Reaction >14 days

5.5.9.1.1.2. Adverse Events Related to Injection Sites

Adverse events related to injection sites will be defined using terms from the MedDRA High Level Term injection site reactions.

The number and percentage of patients with TEAEs related to injection sites, SAEs related to injection sites, and AEs related to injection sites resulting in study drug discontinuation will be summarized using MedDRA PT. Events will be ordered by decreasing frequency of PT term.

The number and percentage of patients with TEAEs related to injection sites by maximum severity will be summarized by treatment groups using MedDRA PT. For each patient and injection site related event, the maximum severity for the MedDRA level being displayed (PT) is the maximum postbaseline severity observed from all associated LLTs mapping to that MedDRA level.

The number and percentage of patients with TEAEs related to injection sites by timing will be summarized using MedDRA PTs ordered by decreasing frequency. Note the timing of AEs related to injection sites is collected through eCRF and categorized into the same categories as for hypersensitivity events.

5.5.9.1.1.3. Upper Respiratory Tract Infections

Upper respiratory tract infections will be defined using all the PTs from the 2 High Level Terms of “upper respiratory tract infections” and “upper respiratory tract infections NEC” as defined in MedDRA. The number and percentage of patients with TEAEs of upper respiratory tract infections will be summarized by treatment group using MedDRA PTs. Events will be ordered by decreasing frequency in the galcanezumab 300 mg group.

The number and percentage of patients with TEAEs of upper respiratory tract infections by maximum severity will be summarized by treatment group using MedDRA PTs. For each patient and upper respiratory tract infection event, the maximum severity for the MedDRA level being displayed (PT) is the maximum postbaseline severity observed from all associated LLTs mapping to that MedDRA level.

By-subject listings of treatment-emergent upper respiratory tract infections and upper respiratory tract infections leading to study drug discontinuation will be provided.

5.5.9.1.2. *Suicide-Related Thoughts and Behaviors*

Postbaseline suicidal ideation, suicidal behavior, and self-injurious behavior without suicidal intent occurring during SP III, based on the C-SSRS, will be summarized by treatment. In particular, for each of the following events, the number and percent of patients with the event will be enumerated by treatment: completed suicide, nonfatal suicide attempt, interrupted attempt, aborted attempt, preparatory acts or behavior, active suicidal ideation with specific plan and intent, active suicidal ideation with some intent to act without specific plan, active suicidal ideation with any methods (no plan) without intent to act, nonspecific active suicidal thoughts, wish to be dead, and self-injurious behavior without suicidal intent. These measures will also be summarized for SP IV.

In addition, the number and percent of patients who experienced at least 1 of various composite measures during SP III and SP IV separately will be presented and compared. These include suicidal behavior (completed suicide, nonfatal suicidal attempts, interrupted attempts, aborted attempts, and preparatory acts or behavior), suicidal ideation (active suicidal ideation with specific plan and intent, active suicidal ideation with some intent to act without specific plan, active suicidal ideation with any methods [no plan] without intent to act, nonspecific active suicidal thoughts, and wish to be dead), and suicidal ideation or behavior.

The number and percent of patients who experienced at least 1 of various comparative measures during treatment will be presented and compared for SP III and SP IV. These include treatment-emergent suicidal ideation compared to recent history, treatment-emergent serious suicidal ideation compared to recent history, emergence of serious suicidal ideation compared to recent history, improvement in suicidal ideation at endpoint compared to baseline, and emergence of suicidal behavior compared to all prior history.

Specifically, the following outcomes are C-SSRS categories and have binary responses (yes/no). The categories have been re-ordered from the actual scale to facilitate the definitions of the composite and comparative endpoints, and to enable clarity in the presentation of the results.

Category 1 – Wish to be Dead

Category 2 – Nonspecific Active Suicidal Thoughts

Category 3 – Active Suicidal Ideation with Any Methods (Not Plan) without Intent to Act

Category 4 – Active Suicidal Ideation with Some Intent to Act, without Specific Plan

Category 5 – Active Suicidal Ideation with Specific Plan and Intent

Category 6 – Preparatory Acts or Behavior

Category 7 – Aborted Attempt

Category 8 – Interrupted Attempt

Category 9 – Actual Attempt (Non-Fatal)

Category 10 – Completed Suicide

Self-injurious behavior without suicidal intent is also a C-SSRS outcome (although not suicide related) and has a binary response (yes/no).

Composite endpoints based on the above categories are defined below.

- Suicidal ideation: A “yes” answer at any time during treatment to any 1 of the 5 suicidal ideation questions (Categories 1 to 5) on the C-SSRS.
- Suicidal behavior: A “yes” answer at any time during treatment to any 1 of the 5 suicidal behavior questions (Categories 6 to 10) on the C-SSRS.
- Suicidal ideation or behavior: A “yes” answer at any time during treatment to any 1 of the 10 suicidal ideation and behavior questions (Categories 1 to 10) on the C-SSRS.

The following outcome is a numerical score derived from the C-SSRS categories. The score is created at each assessment for each patient and is used for determining treatment emergence.

- Suicidal Ideation Score: The maximum suicidal ideation category (1 to 5 on the C-SSRS) present at the assessment. Assign a score of 0 if no ideation is present.

For SP III and SP IV only, comparative endpoints of interest are defined below. “Treatment emergence” is used for outcomes that include events that first emerge or worsen. “Emergence” is used for outcomes that include events that first emerge.

- Treatment-emergent suicidal ideation compared to recent history:
An increase in the maximum suicidal ideation score during treatment (Visits 3.01 to 7 for SP III; Visits 7.01 to 9 for SP IV) from the maximum suicidal ideation category during the screening and lead-in periods (C-SSRS scales taken at Visits 1 to 3 excluding “lifetime” for SP III; C-SSRS scales taken at Visits 1 to 7 excluding “lifetime” for SP IV).
- Treatment-emergent suicidal ideation compared to all prior history:
An increase in the maximum suicidal ideation score during treatment (Visits 3.01 to 7 for SP III; Visits 7.01 to 9 for SP IV) from the maximum suicidal ideation category prior to treatment (C-SSRS scales taken at Visits 1 to 3 including “lifetime” for SP III; C-SSRS scales taken at Visits 1 to 7 including “lifetime” for SP IV).
- Treatment-emergent serious suicidal ideation compared to recent history:
An increase in the maximum suicidal ideation score to 4 or 5 on the C-SSRS during treatment (Visits 3.01 to 7 for SP III; Visits 7.01 to 9 for SP IV) from not having serious suicidal ideation (scores of 0 to 3) during the screening and lead-in periods (C-SSRS scales taken at Visits 1 to 3 excluding “lifetime” for SP III; C-SSRS scales taken at Visits 1 to 7 excluding “lifetime” for SP IV).
- Treatment-emergent serious suicidal ideation compared to all prior history:
An increase in the maximum suicidal ideation score to 4 or 5 on the C-SSRS during treatment (Visits 3.01 to 7 for SP III; Visits 7.01 to 9 for SP IV) from not having serious suicidal ideation (scores of 0 to 3) prior to treatment (C-SSRS scales taken at Visits 1 to 3 including “lifetime” for SP III; C-SSRS scales taken at Visits 1 to 7 including “lifetime” for SP IV). Emergence of serious suicidal ideation compared to recent history:
- An increase in the maximum suicidal ideation score to 4 or 5 on the C-SSRS during treatment (Visits 3.01 to 7 for SP III; Visits 7.01 to 9 for SP IV) from no suicidal ideation (scores of 0) during the screening and lead-in periods (C-SSRS scales taken at Visits 1 to 3 excluding “lifetime” for SP III; C-SSRS scales taken at Visits 1 to 7 excluding “lifetime” for SP IV). Recent history excludes “lifetime” scores from the Baseline C-SSRS scale or Baseline/Screening C-SSRS scale.
- Emergence of serious suicidal ideation compared to all prior history:
An increase in the maximum suicidal ideation score to 4 or 5 on the C-SSRS during treatment (Visits 3.01 to 7 for SP III; Visits 7.01 to 9 for SP IV) from no suicidal ideation (scores of 0) prior to treatment (C-SSRS scales taken at Visits 1 to 3 including “lifetime” for SP III; C-SSRS scales taken at Visits 1 to 7 including “lifetime” for SP IV).

- Improvement in suicidal ideation at endpoint compared to baseline: A decrease in suicidal ideation score at endpoint (the last measurement during treatment; Visits 3.01 to 7 for SP III; Visits 7.01 to 9 for SP IV) from the baseline measurement (the measurement taken just prior to that study phase (last nonmissing value taken at Visit 2 to Visit 3 for SP III; last nonmissing value taken at Visit 3.01 to Visit 7 for SP IV)).
- Emergence of suicidal behavior compared to all prior history: The occurrence of suicidal behavior (Categories 6 to 10) during treatment (Visits 3.01 to 7 for SP III; Visits 7.01 to 9 for SP IV) from not having suicidal behavior (Categories 6 to 10) prior to treatment (Visits 1 to 3 including “lifetime” for SP III; C-SSRS scales taken at Visits 1 to 7 including “lifetime” for SP IV).

Patients who discontinued from the study with no postbaseline C-SSRS value will be considered unevaluable for analyses of suicide-related events. Only evaluable patients will be considered in the analyses. Fisher’s exact test will be used for treatment comparisons in SP III.

